### 2.3.2 Secondary Endpoints

#### 2.3.2.1 Technical Success

Technical success is defined as successful aneurysmal exclusion using the GORE® VIABAHN® Endoprosthesis at time of the procedure without Type I or III endoleaks that require post-procedure intervention within 30 days.

#### 2.3.2.2 Freedom from limb loss on the study limb

Limb loss is defined as an amputation on the study limb above the metatarsals. Freedom from limb loss on the study limb at 12, 24, and 36 months after implant will be estimated by time-to-event analysis.

#### 2.3.2.3 Freedom from repeat intervention

Re-intervention is defined as an endovascular or surgical procedure performed to treat a stenosis or occlusion within the study device(s) or within 5 mm of the proximal or distal edge of the device(s), treatment of endoleaks or other reasons. Freedom from repeat intervention at 12, 24, and 36 months after implant will be estimated by time-to-event analysis.

#### 2.3.2.4 Length of procedural hospital stay

The length of hospital stay is defined as the number of days the subject remains in the hospital due to endovascular repair of a PAA with VIABAHN (“index procedure”).

### 2.3.2.5 Length of procedure

The length of the procedure is defined as the number of minutes the subject remains in the operating room or catheterization laboratory due to endovascular repair of a PAA. If no specific information is available the first and last angiographic timestamp can be used to capture the length of the procedure.

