3.3. Study Endpoints

3.3.1. Definitions

Acute Limb Ischemia[55]: Defined by the operating or treating physician. Typically defined as emergently threatened, whether marginally or immediately, implying reversible ischemia in a limb that is salvageable without a major amputation if arterial obstruction is relieved quickly or irreversible ischemic change requiring major amputation.

Adverse Event (AE): Any untoward medical occurrences, unintended disease or injury or any untoward clinical signs (including abnormal laboratory findings) in patients, users or other persons related to the investigational medical device or procedure.[56] For this study, only device or procedure related AEs need to be reported.

Device Fracture: A stent fracture was defined as any discontinuity of the normal structure of the stent as diagnosed on x-ray.

Endoleak (Modified from White et al.)[57]:

Type I – Present when a persistent perigraft channel of blood flow develops due to inadequate or ineffective seal at the graft ends.

Type II – Occurs when there is persistent collateral blood flow into the aneurysm sac flowing retrogradely from collateral branches.

Type III – Arises at the mid-graft region due to leakage through a defect in the graft fabric or between the segments of multiple grafts.

Type IV –Blood diffusion across the pores of the graft fabric or through tiny holes in the graft fabric caused by sutures or stent struts.

Type V - Leakage from an unknown origin.

Hinge Point: Located at the adductor tubercle, which corresponds to the upper border of the patella, in a plane perpendicular to the femoral axis.

Length of Hospital Stay: The number of days the subject remains in the hospital due to endovascular repair of a PAA with VIABAHN (“index procedure”).

Length of Procedure: The number of minutes the subject remains in the operating room or catheterization laboratory due to endovascular repair of a PAA. If no specific information is available the first and last angiographic timestamp can be used to capture the length of the procedure.

Limb Loss: An amputation on the study limb above the metatarsals.

Migration: Any post-operative device migration requiring treatment.

Patency:

Primary Patency: Blood flow without occlusion maintained through the device after implant without an intervention.

Primary Assisted Patency: Blood flow maintained through the device after implant regardless of re-interventions performed (without occlusion).

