3.3.3. Secondary Endpoints

The secondary endpoints for this trial are:

- Technical success;
- Freedom from limb loss on the study limb at 12, 24 & 36 months;

CONFIDENTIAL INFORMATION

MD133246 Protocol Template

Revision#: 1

Doc Type: GC

- Freedom from repeat intervention at 12, 24 & 36 months;
- Length of procedural hospital stay in days;
- Length of procedure in minutes;
- Serious adverse events and adverse events related to the study procedure or study device at 24 & 36 months;
- Primary patency at 24 & 36 months;
- Primary assisted patency at 12, 24 & 36 months;
- Secondary patency at 12, 24 & 36 months.

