5.5. Procedure

As part of the retrospective study the subject previously received the study device. Procedural information related to placement of the device(s) such as overlap, oversizing, number of devices, landing zone, post-deployment dilatation, SAEs, and AEs related to the initial study procedure or the study device will be recorded on the Case Report Forms (CRFs), as available.

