## 5.5 Secondary Endpoints

**Primary patency**, which is defined as blood flow maintained through the device without an intervention. Blood flow should be determined at the follow-up visits, by either angiography or color-coded duplex sonography. In the event that duplex sonography is not obtained, blood flow will be assessed by clinician exam. Primary patency at 12, 24, & 36 months after implant will be estimated through time-to-event analysis.

**Serious adverse events and adverse events** relative to the study device and procedure will be obtained through 36 months for assessment of the device safety. Counts will be tabulated at 24, & 36 months.

**Length of hospital stay** will be measured in calendar days. Length of hospital stay will be calculated omitting all patients with unknown endpoint status.

**Length of procedure** will be measured in minutes. Length of procedure will be calculated omitting all patients with unknown endpoint status.

**Primary assisted patency** at 12, 24, & 36 months after implant will be estimated through time-to-event analysis. Blood flow should be determined by angiography or color-coded duplex sonography. In the event that duplex sonography is not obtained, blood flow will be assessed by clinician exam.

**Freedom from limb loss** of the study limb at 12, 24, & 36 months after implant will be estimated through time-to-event analysis.

**Freedom from repeat intervention** at 12, 24, & 36 months after implant will be estimated through time-to-event analysis.

**Secondary patency** at 12, 24, & 36 months after implant will be estimated through time-to-event analysis. Blood flow should be determined by angiography or color-coded duplex sonography. In the event that duplex sonography is not obtained, blood flow will be assessed by clinician exam.

**Technical Success** is defined as successful aneurysmal exclusion using the GORE® VIABAHN® Endoprosthesis at time of the procedure without Type I and III endoleaks that require post-procedure intervention within 30 days. All subjects without known status for this endpoint will be omitted in calculating this statistic.

In addition, listings of the following events will be provided: endoleak, migration, fracture, and amputation.

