## 8.0 Data Sets, Tables, Figures, and Listings

### 8.1 Analysis Tables

- Subject Demographics (Sex, Age)
- Subject Medical History (Smoking History, Diabetes Mellitus, Hypertension, Hyperlipidemia, Stroke, Coronary Artery Disease, Myocardial Infarction, Congestive Heart Failure, Deep Vein Thrombosis, Bilateral Popliteal Artery Aneurysm, History of Abdominal Aortic, Iliac, or SFA Aneurysm)
- Summary of Enrollment by Site (Number of Subjects Enrolled at Each Site)
- Summary of Pre-Procedure (Study Limb, Pre-Procedure Resting ABI, Runoff Vessels in Study Limb, Pedal Pulses Present in Study Limb, Aneurysm Diameter, Symptomatic Due to Aneurysm, Aneurysm Length, Mural Thrombus Present, Thrombus Diameter)
- Summary of Procedure (Length of Procedure Time, Successful Deployment, Post-deployment Dilation of Device(s) Performed, Additional Inflow/Outflow Procedures Performed, Additional Procedures Performed at Study Aneurysm Site, Post-procedure Resting ABI, Successful Aneurysmal Exclusion, Length of Hospital Stay)

- Summary of Device Use (Number of Devices Implanted, Length of Device Overlap, Device Diameter, Device Length)
- Medications (Aspirin, Clopidogrel, Prasugrel, Ticlopidine, Warfarin, Other)
- Primary Patency at 12 Months
- Primary Safety at 12 Months
- Kaplan-Meier Estimates of Primary Patency (Primary Patency by Time Post Treatment)
- Counts of Serious Adverse Events and Adverse Events Relative to the Study Device and Procedure at 24 and 36 Months After Procedure
- Kaplan-Meier Estimates of Primary Assisted Patency (Primary Assisted Patency by Time Post Treatment)
- Kaplan-Meier Estimates of Freedom From Limb Loss (Freedom From Limb Loss by Time Post Treatment)
- Kaplan-Meier Estimates of Freedom From Repeat Intervention (Freedom From Repeat Intervention by Time Post Treatment)
- Kaplan-Meier Estimates of Secondary Patency (Secondary Patency by Time Post Treatment)
- Technical Success at 30 Days
- Summary of All Adverse Events by MedDRA SOC, HLT, PT and Follow-up Interval
- Summary of Serious Adverse Events by MedDRA SOC, HLT, PT and Follow-up Interval
- Summary of Device and Procedure Related Adverse Events by MedDRA SOC, HLT, PT and Follow-up Interval
- Summary of Device and Procedure Related Serious Adverse Events by MedDRA SOC, HLT, PT and Follow-up Interval
- Summary of Subject Follow-Up (Subject Follow-Up by Interval)

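### Length of procedure lets a shorter angiogram-to-angiogram interval stand in for room time, and the plan requires neither a source flag nor a separate summary

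*SAP*

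**What the plan says.** Procedure length is a named secondary endpoint (Protocol 3.3.3: "Length of procedure in minutes"). SAP 2.3.2.5 defines it as "the number of minutes the subject remains in the operating room or catheterization laboratory due to endovascular repair of a PAA", and Protocol 3.3.1 uses the same definition. Both documents then add the same fallback: "If no specific information is available the first and last angiographic timestamp can be used to capture the length of the procedure".

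The analysis rule is short. SAP 5.5 says "Length of procedure will be measured in minutes" and "Length of procedure will be calculated omitting all patients with unknown endpoint status"; Protocol 10.3.5 matches it. Neither names a summary statistic. The table plan in SAP 8.1 has one item for the endpoint, inside "Summary of Procedure (Length of Procedure Time, Successful Deployment" and the rest of that line. Nothing in these sections asks for the source of the time, a count by source, a separate row or a sensitivity analysis.

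Procedural data are retrospective. Protocol 5.5 says such information "will be recorded on the Case Report Forms (CRFs), as available".

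**The concern.** The definition and the fallback measure different things. Room time runs from entry to exit. The angiographic interval starts at the first run and stops at the last, so it leaves out whatever happens in the room before and after imaging, such as preparation, access and closure. A fallback value counts as known under the omission rule, so it enters the same summary as the room times.

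The error runs in one direction, and enrolling more patients would not remove it. A reader given a single figure could not tell how many values were of each kind, and so could not correct for it. With no control arm, outside figures are the main thing this number could be set against. Protocol 1.2 cites shorter operative times as an advantage of endovascular repair, which is why a downward shift deserves attention.

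**Working it through.** The documents state no expected procedure length, spread, fallback share or gap, so there is no figure of theirs to reproduce. The check is an identity followed by a range of assumed inputs.

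**Identity.** Let R be room time, A the last minus the first angiographic timestamp, f the share of analysed records that use A, and g the mean of R − A in those records.

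- Pooled mean = mean(R) − f × g, so the shift is −f × g.
- If all index angiograms are taken while the patient is in the room, A ≤ R for every patient. Then g ≥ 0 and the shift is never upward.
- If f = 0, the shift is 0 whatever the gap.

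**Proportional illustration.** Assume a mean room time of 120 minutes and A = r × R with r between 0.5 and 0.7, so g is 60 to 36 minutes. Pooled mean = 120 × (1 − f) + 120 × r × f.

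| Share f | r = 0.5 | r = 0.7 | Shortfall |
|---|---|---|---|
| 0 | 120 | 120 | 0% |
| 0.1 | 108 + 6 = 114 | 108 + 8.4 = 116.4 | 3-5% |
| 0.3 | 84 + 18 = 102 | 84 + 25.2 = 109.2 | 9-15% |
| 0.5 | 60 + 30 = 90 | 60 + 42 = 102 | 15-25% |

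**Share and gap both matter.** With f fixed at 0.3, a gap of 15 minutes gives −0.3 × 15 = −4.5 minutes and a gap of 60 gives −0.3 × 60 = −18 minutes, a fourfold difference at the same share.

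**Scale against sampling error.** With n = 50 and an assumed SD of 30 to 60 minutes, the 95% half-width of a mean is 1.96 × 30/√50 = 8.3 to 1.96 × 60/√50 = 16.6 minutes. At f = 0.1 the shift for gaps of 15 to 60 minutes is 1.5 to 6 minutes, inside that range. At f = 0.5 it is 7.5 to 30 minutes and can exceed it.

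**If a median is reported.** The shift is still downward but is not f × g. In a simulation with lognormal room times (mean 120, SD 45), f = 0.3 and g = 60, the median moved by −13.8 minutes and the mean by −17.9.

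**Does using room times alone remove the problem?** Only if room time is missing independently of procedure length. Take the same assumed distribution and let the chance of needing the fallback rise in proportion to R, averaging 0.3. Then mean(R²) = 120² + 45² = 16,425, and the mean among records with room time is (120 − 0.3 × 16,425/120)/0.7 = (120 − 41.1)/0.7 = 112.8, a shift of −7.2 minutes. Pooling with g = 30 gives −0.3 × 30 = −9.0. Restriction helps little in that case. If missingness is unrelated to length, restriction has no bias.

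**The case against.** The fallback is conditional and optional, and it is prespecified identically in both documents. That is a reasonable way to rescue values from retrospective records. If every site has room times, no record uses it and nothing is wrong. This stands: the documents make some fallback use plausible but do not establish it, so the point must be conditional.

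Pooling without distinction is also partly an inference. The CRF is not among the documents and may already capture the source, and SAP 7.1 and 7.2 leave input fields and footnotes to separate specifications. What can be said is that the protocol and SAP text does not require a flag or a split.

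Three stronger readings are tempting and are not supported:

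- A reader might infer that the reported mean is biased low by an amount set by the fallback share. No mean is specified, the bias exists only if the fallback is used, and its size depends on the gap as much as on the share.
- A reader might infer that the figure will differ between sites according to record quality. Nothing in the documents describes site record quality, and no site comparison of this endpoint is listed.
- A reader might infer that a comparison with published times will favour the device. No such comparison is planned in the readable text, and Protocol 1.2 does not say how the operative times it cites were measured. Whether mixing the two intervals worsens or reduces a mismatch with them cannot be determined.

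**Conclusion.** The point holds as a conditional one. Relative to the plan's own room-time definition, any fallback record can only lower the summary, and the plan as written would not let a reader see by how much. This rests on index angiograms being taken while the patient is in the room.

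The size cannot be computed from the documents. The shortfalls tabulated above, from nil to 25%, depend entirely on the assumed 120 minutes, the 50-70% span and the assumed shares.

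The consequence is limited. This is a descriptive secondary endpoint in a single-arm study, and no test or primary conclusion in the readable text depends on it. It is a cheap improvement to a reported figure and does not threaten the study's findings.

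**What to change.** Record for each patient whether the time came from room records or angiographic timestamps, and report the count of each. In the SAP 8.1 procedure table, make room time the main length-of-procedure result and give the angiographic span its own row with its own n. Do not pool the two. State in SAP 5.5 which summary statistic will be used.

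Add a footnote that the room-time row is unbiased only if room time is missing independently of procedure length. For that reason the angiographic row should be kept and shown, not dropped.

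The cost is one source flag, one table row and a smaller n for the room-time summary.

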### 2.3.2.6 Serious adverse events and adverse events related to the study procedure or study device at 24 and 36 months

### 2.3.2.7 Primary patency at 24 and 36 months

Primary patency at 12, 24, and 36 months after implant will be estimated by time-to-event analysis.

### 2.3.2.8 Primary assisted patency

Primary assisted patency is defined as blood flow maintained through the device after implant regardless of re-interventions performed (without occlusion). Primary assisted patency at 12, 24, and 36 months after implant will be estimated by time-to-event analysis.

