Study Endpoints	
The primary performance endpoint for this trial is:
 
 • Primary patency at 12 months 
The primary safety endpoint of this trial is:
 
 • 12 month serious adverse events and adverse events related to the study procedure or the study device. 
The secondary endpoints of this trial are:
 
 • Serious adverse events and adverse events related to the study procedure or the study device at 24 & 36 months; • Freedom from limb loss on the study limb through 12, 24 & 36 months; • Freedom from repeat intervention at 12, 24 & 36 months; • Length of hospital stay after procedure in days; • Length of procedure in minutes; • Primary patency at 24 & 36 months; • Primary assisted patency at 12, 24 & 36 months; • Secondary patency at 12, 24 & 36 months. • Technical Success 
Listings:

CONFIDENTIAL INFORMATION

	Listings of the following events will be provided: endoleak, migration, device fracture, and study limb amputation.
Subject Population	The study population includes patients with a symptomatic aneurysm or asymptomatic aneurysm (≥ 2 cm diameter) of the popliteal artery, or presence of mural thrombus (< 2 cm) in the popliteal artery. All patients treated per IFU with the GORE® VIABAHN® Endoprosthesis since September 15, 2012 (date of reimbursement in France) will be screened consecutively, starting with the first patient treated.
Number of Patients	Patients meeting Inclusion / Exclusion that provided Informed Consent will be enrolled in consecutive order. 50 patients with adequate follow-up to determine primary endpoints through 12 months will be enrolled. For patients that cannot be enrolled, but had a PAA treated with VIABAHN in the respective time, the date of the intervention and the reasons for non-inclusion will be collected in a screen-failure CRF.
Number of Sites	Up to 10 Sites in France.
Expected Time to Complete Enrollment	Patient identification / enrollment is expected to take up to 9 months. Patients follow-up will continue to collect 36 months data.
Schedule of Events	All patients will be followed up as per hospital standard of care for the duration of the study. As available, data will be collected on adverse events, ankle brachial index, palpable pedal pulses, medications, imaging, all re-interventions, and bypass surgeries.

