Secondary Patency: Blood flow through the device regardless of re-interventions performed (with or without occlusion) and freedom from surgical bypass.

Re-intervention: Endovascular or surgical procedure performed to treat a stenosis or occlusion within the study device(s) or within 5 mm of the proximal or distal edge of the device(s), treatment of endoleaks or other reasons.

Serious Adverse Event (SAE)[56]: An AE that led to death or lead to serious deterioration in the health of the subject that resulted in a life threatening illness or injury, or a permanent impairment of a body structure of body function, or in-patient or prolonged hospitalization, or a medical or surgical intervention to prevent life-threatening illness or injury, or permanent impairment to a body structure or a body function.

Technical Success: Successful aneurysmal exclusion using the GORE® VIABAHN® Endoprosthesis at time of the procedure without Type I or III endoleaks that require post-procedure intervention within 30 days.

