5.9. Subject Study Completion

A subject has completed the study when 36 months (1185 days or 3x365 + 90 days) of follow-up data has been recorded on the CRFs. Any subject that does not complete these requirements due to voluntary withdrawal, death, lost secondary patency (e.g. had a study limb bypass) or any other reason will be considered a withdrawal and the reason for discontinuation will be marked on the CRF.

If a subject is lost to follow-up, the appropriate CRF must be completed as soon as possible after subject status has been determined. If a subject fails to comply with follow-up evaluations, the Site must make at least three attempts to contact the patient and his family and potentially his General Practitioner. Each attempt to contact the subject and the method used (e.g., telephone contact, registered letter) must be documented in the subject's records.

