### 2.3.2.9 Secondary patency

Secondary patency is defined as blood flow through the device regardless of re-interventions performed (with or without occlusion) and freedom from surgical bypass. Secondary patency at 12, 24, and 36 months after implant will be estimated by time-to-event analysis.

[REDACTED]

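### Primary assisted patency has no bypass condition although secondary patency does, so bypass of a flowing, never-occluded device is no assisted-patency event and the estimate can be too high

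*SAP*

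**What the plan says.** - **Primary assisted patency.** SAP 2.3.2.8: "Primary assisted patency is defined as blood flow maintained through the device after implant regardless of re-interventions performed (without occlusion". Protocol 3.3.1 uses the same terms: "Blood flow maintained through the device after implant regardless of re-interventions performed (without occlusion". Bypass appears in neither.
- **Secondary patency.** Protocol 3.3.1 and SAP 2.3.2.9 forgive occlusion as well but add a condition: "regardless of re-interventions performed (with or without occlusion) and freedom from surgical bypass".
- **Primary patency.** SAP 2.3.1.1 and Protocol 3.3.1 require flow without occlusion and without any intervention.
- **Re-intervention.** Protocol 3.3.1 starts with "Endovascular or surgical procedure performed to treat a stenosis or occlusion within the study device(s" and extends to the device edges, endoleak treatment and other reasons. The Schedule of Events entry in the Protocol Summary, however, names "all re-interventions, and bypass surgeries" as separate items to collect.
- **Handling of a bypassed patient.** Protocol 5.9 counts as a withdrawal any subject who "lost secondary patency (e.g. had a study limb bypass", and SAP 8.1 tabulates surgical bypass as a discontinuation category.
- **Estimator.** SAP 8.1 plans Kaplan-Meier tables for all three patency tiers. No section says whether bypass is an event, a censoring time or neither for assisted patency.

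**The concern.** Each tier is meant to forgive more than the one before: primary forgives nothing, assisted forgives re-intervention on an open device, and secondary also forgives occlusion. One would expect primary ≤ assisted ≤ secondary. Here the most forgiving tier carries a failure condition that the middle tier lacks.

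The case that falls through is a device that is stenosed or leaking, has never occluded, still carries flow, and is then bypassed. The documents foresee the ingredients: Protocol section 8 lists stenosis, endoleak and open surgical conversion among the risks, and bypass surgeries are to be collected. Such a patient fails primary and secondary patency but has no event for assisted patency. If the patient is censored at bypass, that censoring is probably informative, because the patient leaves at the moment the device needed surgical rescue.

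At stake are the assisted-patency estimates at 12, 24 and 36 months and their ordering against secondary patency. Different programmers could also code the same bypass as ignored, censored or failed without contradicting the text.

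**Working it through.** **Step 1: compare the definitions for one patient** (bypass, flow through the device persists, never occluded).

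| Tier | Text that decides | Result |
|---|---|---|
| Primary | no intervention allowed | fails |
| Assisted, if bypass is a re-intervention | re-interventions forgiven, no occlusion | no event |
| Assisted, if bypass is not a re-intervention | definition silent on bypass | no event |
| Secondary | freedom from surgical bypass required | fails |

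The unclear status of bypass as a re-intervention does not change the result: on neither reading is it an assisted-patency event.

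**Step 2: size.** The documents state no assisted or secondary patency figure to reproduce and no bypass count. The following is an illustration.

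Inputs: N = 50 (SAP 2.2). Assumed: o = 5 occlusions by 12 months or 10 by 36 months; b = 1, 2, 3 or 5 bypasses of a flowing, never-occluded device, all before the first occlusion; no other losses.

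- Bypass ignored: (50 − o)/50
- Bypass censored: (50 − b − o)/(50 − b)
- Bypass counted as failure: (50 − o − b)/50

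Example, o = 5 and b = 1: 45/50 = 90.0%; 44/49 = 89.8%; 44/50 = 88.0%.

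| b | 12 months, o = 5: ignored / censored / failure | 36 months, o = 10: ignored / censored / failure |
|---|---|---|
| 1 | 90.0 / 89.8 / 88.0 | 80.0 / 79.6 / 78.0 |
| 2 | 90.0 / 89.6 / 86.0 | 80.0 / 79.2 / 76.0 |
| 3 | 90.0 / 89.4 / 84.0 | 80.0 / 78.7 / 74.0 |
| 5 | 90.0 / 88.9 / 80.0 | 80.0 / 77.8 / 70.0 |

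Ignored minus failure is b/50, or 2 points per bypass. Censored minus failure is (b/50) × (50 − b − o)/(50 − b), which is 2 points times the censored estimate: 2 × 0.898 = 1.8 at 12 months and 2 × 0.796 = 1.6 at 36 months for b = 1. Later bypasses move the censored result towards 2 points. With one bypass after three of the five occlusions, the estimate is 47/50 × 44/46 = 89.9%, or 1.9 points above 88.0%. With b = 0 all three agree.

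**Step 3: ordering against secondary patency.** At 12 months with o = 5:

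- Two occlusions reopened, three permanent: secondary = (47 − b)/50, giving 92%, 90% and 88% for b = 1, 2 and 3. Assisted is 90.0% if ignored, or 89.8%, 89.6% and 89.4% if censored. It exceeds secondary only from b = 3.
- None reopened: with b = 1, secondary is 44/50 = 88.0% against 90.0% or 89.8% assisted. One such bypass reverses the order.

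At 36 months with o = 10 and five reopened, secondary is (45 − b)/50. Even b = 5 gives 80%, which assisted (80.0% ignored, 77.8% censored) does not exceed.

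**The case against.** A reader might infer more than the documents support.

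- **That the bypassed patient is carried as an assisted-patency success to 36 months.** Protocol 5.9 withdraws that patient. Censoring is the more natural handling, and even that is an inference because no rule is written.
- **That the assisted rate is inflated.** The effect needs at least one bypass that leaves flow through a never-occluded device. A bypass done for occlusion already fails assisted patency, and so does one that ends flow through the device. Protocol 5.11 foresees explant at surgery, and Protocol 1.2 describes ligation as the usual companion of bypass in open repair generally. Persisting flow cannot be assumed.
- **That the gap is 100% assisted against 98% to 92% secondary for one to four such bypasses.** The arithmetic is right but assumes no occlusions at all. Reopened occlusions lower assisted but not secondary patency and can hide or offset the gap, as Step 3 shows.
- **That the tiers cannot be interpreted.** No formal comparison between tiers is planned, and no section promises nesting. SAP 8.1 and 8.2 also show bypasses as discontinuations and list re-interventions, so a reader could see them.

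These points limit the size and certainty of the effect. They do not remove the asymmetry, which is identical in both documents, or the missing rule. It can also be argued that one sentence on event or censoring status would be enough. That would end the ambiguity, but a rule that censored bypass would keep the informative censoring and the possible reversal of order.

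**Conclusion.** The point holds as a defect in a secondary, descriptive endpoint. A bypass of a flowing, never-occluded device is a failure under primary and secondary patency but not under assisted patency, and its handling in the Kaplan-Meier analysis is unwritten. The assisted estimate can therefore be too high and can exceed secondary patency. Under the stated assumptions the excess per bypass is about 1.6 to 1.8 points if censored early, approaching 2 if censored later, and 2 if ignored. Whether any such bypass occurs is unknown from the documents, so an actual bias is possible but not shown. Primary patency at 12 months fails on any intervention and is unaffected.

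**What to change.** 1. In Protocol 3.3.1 and SAP 2.3.2.8, add to primary assisted patency the freedom-from-surgical-bypass condition that secondary patency already has.
2. In the SAP, make the date of a study-limb bypass an event, not a censoring time, in the assisted-patency Kaplan-Meier analysis, and say how this works alongside the withdrawal in Protocol 5.9.
3. State whether a bypass is a re-intervention, so that the Protocol Summary and Protocol 3.3.1 agree. This also settles whether it counts in freedom from repeat intervention.

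The cost is a clause in each document, a sentence on re-intervention and a line in the analysis dataset specification. Bypass surgeries are already among the data to be collected. The downside is a possibly slightly lower assisted-patency figure.
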